8.1.3 Confirmed Response using irRC and irRECIST

Table 7 incorporates the response confirmation rules indicated in the irRC and irRECIST guidelines (see Appendix B and Appendix D).

Table 7 Confirmed Response using irRC or irRECIST

Visit-Level Response	Next Visit-Level Response	Confirmed Response
CR	CR	CR (if visit-level disease assessments are \geq 28 days apart), otherwise SD
CR	PR	PR (if visit-level disease assessments are \geq 28 days apart), otherwise SD
CR	SD	SD
CR, PR, SD	PD	SD
CR, PR	NE	SD
PR	CR, PR	PR (if visit-level disease assessments are \geq 28 days apart); otherwise, SD
PR	SD	SD
SD	SD, CR, PR, PD, NE	SD
PD	PD	PD (if visit-level disease assessments are \geq 28 days apart), otherwise, NE .
CR, PR, SD	No 2 nd visit	SD
PD	No 2 nd visit	NE
NE	No 2 nd visit	NE

The minimum interval for confirmation of CR, PR and PD is 28 days. Subjects must have at least one post-baseline disease assessment to be assigned SD as the best overall response; otherwise, there is no minimum interval for assignment of SD as the best overall response. The same algorithm as for RECIST v1.1 criteria will be used to determine time between disease assessments for confirmation of CR, PR, and PD.

In some situations, it may be necessary to check across more than two sequential time points in order to determine whether or not a minimum duration criteria has been met. The same logic as used for the pairs of time points should be applied. For example, note the following examples.

- For the triplet CR NE CR, if the minimum criteria for CR duration is met for the interval between the two CR assessments, then **Confirmed Response = CR**. Otherwise **Confirmed Response = SD**.
- For the triplet CR CR CR, if the minimum criteria for CR duration is met for the interval between the first and third CR assessments, then **Confirmed Response = CR**. Otherwise **Confirmed Response = SD**.
- For the triplet PR NE PR, if the minimum interval criteria for PR is met for the interval between the two PR assessments, then **Confirmed Response = PR**. Otherwise **Confirmed Response = SD**.
- For the triplet PR PR PR, if the minimum interval criteria for PR is met for the interval between the first and third PR assessments, then **Confirmed Response = PR**. Otherwise **Confirmed Response = SD**.

For confirmed progression using irRC and irRECIST.

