- For the triplet PD NE PD, if the minimum interval criteria for PD is met for the interval between the two PD assessments, then **Confirmed Response = PD**. Otherwise **Confirmed Response = NE**.
- For the triplet PD PD PD, if the minimum interval criteria for PD is met for the interval between the first and third PD assessments but is not met between the first and second PD assessments or between the second and third PD assessments, then **Confirmed Response = PD**. Otherwise **Confirmed Response = NE**.

8.1.4 Derivation of irRECIST Confirmed Response for Phase 1 Subjects Treated at the RP2D

For both combinations, subjects enrolled in the Phase 1 portion of the trial will also be analyzed with the Phase 2 subjects. Therefore, the irRECIST response at each visit, as well as the overall confirmed best response, will be derived. These derived responses will be summarized as described in Section 8.1.3.

Visit 1-Screening:- Derived baseline tumor burden will be the sum of the longest diameters of the lesions that have “Yes” for Baseline Target Lesion. Derived non-target lesions will be all lesions identified on the Non-Measurable Disease Assessment page.

Subsequent disease assessments:- Derived tumor burden will be the sum of the longest diameters of all Baseline Target Lesions and lesions identified as new lesions by “Yes” for “Is this a new lesion?” in the Measurable Disease Assessment page of the eCRF. Derived nadir

tumor burden will be the smallest tumor burden across all previous disease assessments, including baseline. Derived non-target lesions will be all lesions identified on the Non-Measurable Disease Assessment page.

Derived Visit Measurable Response:- Using the derived baseline tumor burden, the percentage change from baseline will be calculated as:

Derived percentage change from baseline:

$$\left[\frac{(\text{Derived visit tumor burden} - \text{Derived baseline tumor burden})}{\text{Derived baseline tumor burden}} \right] * 100\%$$

Using the derived nadir tumor burdens, the percentage change from nadir will be calculated for subjects with non-zero derived nadir:

Derived percentage change from nadir:

$$\left[\frac{(\text{Derived visit tumor burden} - \text{Derived nadir tumor burden})}{\text{Derived nadir tumor burden}} \right] * 100\%$$

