8.5 Efficacy Endpoints

ORR is defined as the proportion subjects with a best confirmed overall response of complete response (CR) or partial response (PR), with assessment of response to be determined by the investigator using irRECIST and RECIST v1.1.

OS is defined as the number of months from initiation of treatment to death from any cause. Subjects who have not died at their last contact will be censored on the date of last contact. The specifications for the time to death calculation are:

- If death is reported either on AE or Death CRF pages, OS will be calculated as *Date of Documentation of (Death – First Dose Date + 1) / 30.4375*.
- Subjects will be censored at their last contact date if death is not reported at the data cut-off date for study closure, and their survival time will be calculated as *(/Last Contact Date - First Dose Date + 1) / 30.4375*). Last contact date is defined as the last date reported among, Adverse Event (AE start date), the Study Exit Status, Hematology, Chemistry, Assessment of RECIST v1.1 Response, Assessment of irRECIST Response, Long Term Follow Up, Study Drug Administration (IMO-2125), ipilimumab Infusion and pembrolizumab Infusion pages of the eCRF.
- Subjects lacking data after the date of first dose who do not die will have their survival time censored on the date of first dose with duration of 1 day.

PFS, defined as number of months from the initiation of treatment to disease progression using RECIST v1.1 or irRECIST or death from any cause, will be calculated as *([Date of Documentation of Death or Disease Progression – First Dose Date + 1]/30.43750*. Subjects without reported progression at their last contact date will be censored on the date of their last valid disease assessment. A valid disease assessment is any disease assessment with overall visit-level response of irCR irPR, irSD, or irPD (without subsequent confirmation) when using irRECIST and CR, PR, or SD when using RECIST v1.1. Subjects who start new anti-cancer therapy before a PFS event will be censored on the date of initiation of new anti-cancer therapy (Subsequent Anti Cancer Therapy eCRF page).

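### Read literally, the PD PD PD bullet in SAP Section 8.1.3 returns NE when both adjacent PD intervals reach 28 days, contradicting Table 7 and Appendix D

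*SAP*

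**What the plan says.** Section 8.1.3 sets the confirmation rules for irRC and irRECIST.

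- **Threshold:** "The minimum interval for confirmation of CR, PR and PD is 28 days".
- **Pairs (Table 7):** PD followed by PD is PD when the assessments are at least 28 days apart, otherwise NE.
- **Link from pairs to triplets:** "The same logic as used for the pairs of time points should be applied".
- **PR triplet:** "For the triplet PR PR PR, if the minimum interval criteria for PR is met for the interval between the first and third PR assessments", the result is PR, otherwise SD. CR CR CR is built the same way. Neither looks at the adjacent intervals.
- **PD triplet:** the outer interval is tested in the same way as for PR, but a second condition on the adjacent intervals is added: "but is not met between the first and second PD assessments or between the second and third PD assessments". All other cases are NE.

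Appendix D asks only that irPD be confirmed by a consecutive assessment at least 4 weeks after it is first documented. In Section 8.5, the visit-level responses that count as valid assessments for censoring PFS include "or irPD (without subsequent confirmation) when using irRECIST".

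**The concern.** The PD triplet has two conditions joined by 'but': the outer interval must pass and the adjacent intervals must fail. Three PDs with long gaps between them are the best-confirmed progressions the schedule can produce. They meet the first condition, fail the second, and drop into the 'Otherwise' branch as NE. PD is confirmed only when the scans are unusually close together, so the rule runs backwards for ordinary data.

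At stake is the split between irPD and NE in the irRECIST best overall response tables, where Section 9.3.1 gives each category an exact 95% confidence interval, and in the Phase 1 irRC listing. For irRECIST PFS and DoR there is a conditional risk: if a programmer takes confirmation from this bullet, a real progression is treated as unconfirmed and censored.

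**Working it through.** **Inputs**

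- Threshold: 28 days (Section 8.1.3).
- Day count: later date minus earlier date plus 1 (Section 8.1.1, carried into 8.1.3).
- Scans: Weeks 8, 17 and 29, each ±7 days (Tables 4 and 5, footnotes). Confirmatory PD scans come at least 4 weeks after first documentation.
- Follow-up scans: at least every 3 months, taken here as 91 days (an assumption).

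**Intervals on schedule**

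- First to second: (17 − 8) × 7 + 1 = 64 days.
- Second to third: (29 − 17) × 7 + 1 = 85 days.
- First to third: (29 − 8) × 7 + 1 = 148 days.
- Tightest windows: 64 − 14 = 50 days and 85 − 14 = 71 days. Both cannot occur in one subject, because Week 17 would have to be both early and late.

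Without the +1, each interval is one day shorter and no result below changes.

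**Rules compared.** Write d12, d23 and d13 for the three intervals. The word 'or' in the clause can be read two ways:

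- Reading A: PD if d13 ≥ 28 and neither d12 nor d23 reaches 28.
- Reading B: PD if d13 ≥ 28 and at least one of d12, d23 falls short of 28.
- Table 7 pairs: PD if d12 ≥ 28 or d23 ≥ 28.
- Clause deleted: PD if d13 ≥ 28.

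| PD sequence | d12 / d23 / d13 | A | B | Table 7 pairs | Clause deleted |
|---|---|---|---|---|---|
| Weeks 8, 17, 29 | 64 / 85 / 148 | NE | NE | PD | PD |
| Tightest first gap | 50 / 85 / 134 | NE | NE | PD | PD |
| Tightest second gap | 78 / 71 / 148 | NE | NE | PD | PD |
| Week 8, +28 days, Week 17 | 29 / 36 / 64 | NE | NE | PD | PD |
| Weeks 17, 29, +91 days | 85 / 92 / 176 | NE | NE | PD | PD |
| Gaps of 14 and 35 days | 15 / 36 / 50 | NE | PD | PD | PD |
| Gaps of 20 and 20 days | 21 / 21 / 41 | PD | PD | NE | PD |
| Gaps of 10 and 10 days | 11 / 11 / 21 | NE | NE | NE | NE |

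**All gaps from 1 to 120 days.** With the +1, a gap of 27 days or more reaches the threshold, which gives 94 qualifying and 26 short values per gap.

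- Both adjacent intervals qualify: 94 × 94 = 8,836 triplets. All are NE on both readings and PD under Table 7.
- Exactly one qualifies: 2 × 94 × 26 = 4,888 triplets. NE on reading A, PD on reading B and under Table 7.
- Neither qualifies: 26 × 26 = 676 triplets. In 351 of them d13 reaches 28 and the bullet gives PD on both readings; in 325 it does not, and every rule gives NE.

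These counts describe how the rule behaves. They are not expected numbers of subjects.

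**Where the result is used**

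- Primary ORR uses RECIST v1.1 and Table 6, so it is not touched.
- irRECIST ORR is unchanged, because PD and NE are both non-response.
- Both PRO groupings in Section 11.4 put PD and NE together.
- irRECIST best overall response reports PD and NE separately, so it can change.
- irRECIST PFS and DoR (Section 8.5) depend on whether irPD is confirmed, but Section 8.5 does not say that confirmation comes from this bullet.

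**The case against.** The best defence is context. Section 8.1.3 offers the triplets as examples for situations where two time points cannot settle whether the minimum interval is met. If an adjacent pair is already 28 days apart, Table 7 has confirmed PD and no three-point check is needed. On that view the clause only says when the check is called for. This is probably what was meant. It does not rescue the wording: the explicit 'Otherwise' branch turns a trigger into a decision rule, and nothing ranks Table 7 above the bullet. Two programmers could each follow the text and disagree.

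The defence also notes that the sequence should be uncommon. Section 3.2.1 ends treatment at unequivocal progression, and Section 3.2.2 ends radiological follow-up off treatment at RECIST v1.1 PD. The usual pattern would be one PD and one confirmatory PD, which Table 7 handles correctly. That stands, and it limits the practical size.

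A reader might infer that the plan necessarily scores clear progression as NE, or necessarily removes irPFS events. The documents support neither. Table 7 gives PD for the same subject, so the plan contradicts itself rather than settling on NE. Section 8.5 has its own censoring rule and does not cite the triplet; a PD followed by another PD at least 28 days later is confirmed under Table 7 and Appendix D.

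**Conclusion.** The point holds as an internal contradiction with a wrong result if the bullet is coded literally. When both adjacent intervals are at least 28 days, which includes every on-schedule triplet, the bullet gives NE on either reading of 'or', while Table 7 gives PD. When only one adjacent interval qualifies, the result depends on how 'or' is read.

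The misclassification in best overall response assumes that the bullet is programmed as written and overrides Table 7. Lost irRECIST PFS or DoR events need the further assumption that confirmation for those endpoints is taken from the same bullet. The primary RECIST v1.1 ORR, the irRECIST ORR and the PRO groupings do not move. The SAP gives no basis for counting subjects with three PD scans; the number is probably small. This should be corrected before programming, but it does not threaten the trial's main conclusion.

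**What to change.** In the PD PD PD bullet of Section 8.1.3, delete "but is not met between the first and second PD assessments or between the second and third PD assessments". The rule then reads: PD if the first-to-third interval is at least 28 days, otherwise NE. It matches the CR CR CR and PR PR PR bullets, agrees with Table 7 whenever an adjacent pair qualifies, and still confirms closely spaced cases such as 20 + 20 days.

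An equivalent general wording is that PD is confirmed if any two PD assessments at least 28 days apart have no response between them other than PD or NE. NE must be allowed, because the bullet just before confirms PD NE PD.

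The cost is one deleted clause and a check that the derivation program follows it.

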Subjects who have a value of 0 mm for their derived nadir and a derived tumor burden of at least 5 mm will have a missing derived percentage change from nadir and the derived visit measurable response will be PD. Subjects who have a value of 0 mm for their derived nadir and a derived tumor burden between 0 mm and 5 mm will have a missing derived percentage change from nadir and the derived visit measurable response will be SD. Subjects with a derived nadir of 0 and a derived tumor burden of 0 will have a derived visit measurable response of CR.

Table 8: Measureable Lesion Evaluation

Response	Description of response
irCR	
• Complete disappearance of all non-lymph node lesions and no new measurable or non-measurable lesions.• All measurable lymph nodes have diameter <10 mm in short axis.
irPR	
• $\geq 30\%$ decrease in tumor burden from baseline.
irSD	
• Not meeting criteria for irCR, irPR, or irPD.
irPD	
• $\geq 20\%$ increase in tumor burden from nadir and tumor burden ≥ 5 mm.

NE	
Assigned if “Unable to evaluate longest diameter” is marked for at least one target lesion in the CRF page RECIST v1.1 measurable disease.
----	--

Derived Visit Non-Measurable Response: If there are no new non-measurable lesions, the derived visit non-measurable response is the Status of Non-Target Lesions from the Assessment of RECIST Response page of the eCRF.

Lymph nodes will be identified from “Location” in the Measurable Disease Assessment page of the eCRF.

Table 9: Non-measurable Lesion Evaluation

Response	Status of Non-measurable Lesion (eCRF)
irCR	
Absent
Non-irCR/Non-irPD	
Stable
irPD	
Unequivocal Progression
Not Done/Not Eavaluable	
Assigned if the RECIST v1.1 non-target lesions response is Not Done or Not Evaluable.

If there have been new non-measurable lesions identified, the derived visit non-measurable response will be irPD if any are assessed with “Unequivocal Progression”.

The derived irRECIST response will be determined based on the following:

Table 10: Overall irRECIST Response

Target Lesion (Tumor burden)	Non-Target Lesions	New Lesions: Non-Target	Overall (Time point) Response
irCR	irCR	No	irCR

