9.3.3 Measurable Disease Assessment

The absolute and percent change from baseline for the sum of longest diameters of the baseline target lesions from measurable tumor assessment CRF page will be listed by dose group for phase 1 subjects and summarized and listed by treatment arm for phase 2 subjects at the Best-case post baseline. The summary may be repeated for injected and non-injected lesions separately.

Waterfall plots of the maximum percentage change from baseline in measurable tumor burden (the sum of the longest diameter) will be produced for the phase 2 results. The bars will not be coded for any factor but the treatment combinations will be distinct colors in the separate figures.

Measurable disease assessment, non-measurable disease assessment, assessment of RECIST v1.1 response, assessment of irRECIST response and assessment of irRC response data will be listed by subject. **Exploratory Analyses**

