Appendix C: RECIST (Response Evaluation Criteria in Solid Tumors) version 1.1 Guidelines

Adapted from E.A. Eisenhauer, et al: New response evaluation criteria in solid tumors: Revised RECIST guideline (version 1.1). European Journal of Cancer 45 (2009) 228–247.⁵²

A. Categorizing Lesions at Baseline

1. Measurable Lesions

Lesions that can be accurately measured in at least one dimension.

- Lesions with longest diameter twice the slice thickness and at least 10 mm or greater when assessed by CT or MRI (slice thickness 5-8 mm).
- Lesions with longest diameter at least 20 mm when assessed by Chest X-ray.
- Superficial lesions with longest diameter 10 mm or greater when assessed by caliper.
- Malignant lymph nodes with the short axis 15 mm or greater when assessed by CT.

NOTE: The shortest axis is used as the diameter for malignant lymph nodes, longest axis for all other measurable lesions.

2. Non-measurable Disease

- Non-measurable disease includes lesions too small to be considered measurable (including nodes with short axis between 10 and 14.9 mm) and truly non-measurable disease such as pleural or pericardial effusions, ascites, inflammatory breast disease, leptomeningeal disease, lymphangitic involvement of skin or lung, clinical lesions that cannot be accurately measured with calipers, abdominal masses identified by physical exam that are not measurable by reproducible imaging techniques.
- Bone disease: Bone disease is non-measurable with the exception of soft tissue components that can be evaluated by CT or MRI and meet the definition of measurability at baseline.
- Previous local treatment: A previously irradiated lesion (or lesion patient to other local treatment) is non-measurable unless it has progressed since completion of treatment.

3. Normal Sites

- Cystic lesions: Simple cysts should not be considered as malignant lesions and should not be recorded either as target or non-target disease. Cystic lesions thought to represent cystic metastases can be measurable lesions, if they meet the specific

definition above. If non-cystic lesions are also present, these are preferred as target lesions.

- Normal nodes: Nodes with short axis <10 mm are considered normal and should not be recorded or followed either as measurable or non-measurable disease.

4. Recording Tumor Assessments

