Disease sites must be assessed using the same technique as baseline, including consistent administration of contrast and timing of scanning. If a change needs to be made the case must be discussed with the radiologist to determine if substitution is possible. If not, subsequent objective statuses are indeterminate.

1. Target Disease

- Complete Response (CR): Complete disappearance of all target lesions with the exception of nodal disease. All target nodes must decrease to normal size (short axis <10 mm). All target lesions must be assessed.
- Partial Response (PR): Greater than or equal to 30% decrease under baseline of the sum of diameters of all target measurable lesions. The short diameter is used in the sum for target nodes, while the longest diameter is used in the sum for all other target lesions. All target lesions must be assessed.
- Stable: Does not qualify for CR, PR or Progression. All target lesions must be assessed. Stable can follow PR only in the rare case that the sum increases by less than 20% from the nadir, but enough that a previously documented 30% decrease no longer holds.
- Objective Progression (PD): 20% increase in the sum of diameters of target measurable lesions above the smallest sum observed (over baseline if no decrease in the sum is observed during therapy), with a minimum absolute increase of 5 mm.
- Indeterminate. Progression has not been documented, and
 - one or more target measurable lesions have not been assessed;
 - or assessment methods used were inconsistent with those used at baseline;
 - or one or more target lesions cannot be measured accurately (eg, poorly visible unless due to being too small to measure);
 - or one or more target lesions were excised or irradiated and have not reappeared or increased.

2. Non-target Disease

- CR: Disappearance of all non-target lesions and normalization of tumor marker levels. All lymph nodes must be 'normal' in size (<10 mm short axis).
- Non-CR/Non-PD: Persistence of any non-target lesions and/or tumor marker level above the normal limits.

- PD: Unequivocal progression of pre-existing lesions. Generally the overall tumor burden must increase sufficiently to merit discontinuation of therapy. In the presence of SD or PR in target disease, progression due to unequivocal increase in non-target disease should be rare.

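### Sections 8.1.4, 9.1 and 9.3.3 sum longest diameters with no exception for lymph nodes, whereas Appendix C sums the nodal short axis; derived irPR and irPD calls and tumour-change displays can shift in either direction

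*SAP*

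**What the plan says.** Section 8.1.4 of the SAP derives irRECIST responses for Phase 1 subjects treated at the RP2D, so that they can be analysed together with the Phase 2 subjects.

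- **Baseline burden (8.1.4):** "Derived baseline tumor burden will be the sum of the longest diameters of the lesions" flagged as baseline targets.
- **Visit burden (8.1.4):** "Derived tumor burden will be the sum of the longest diameters of all Baseline Target Lesions and lesions identified as new lesions by" a positive answer to the new-lesion item on the measurable disease page. The nadir is the smallest earlier burden, baseline included.
- **Tumour-change summary (9.3.3):** "The absolute and percent change from baseline for the sum of longest diameters of the baseline target lesions". The waterfall plot in that section and the Phase 1 listing in Section 9.1 use the same sum.

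None of these places treats nodes differently. Appendix C does. Its definition of measurable lesions says "The shortest axis is used as the diameter for malignant lymph nodes, longest axis for all other measurable lesions". Its target-lesion rule has the short axis recorded for pathological nodes and builds the baseline sum from it. Its response rule repeats that "The short diameter is used in the sum for target nodes, while the longest diameter is used in the sum for all other target lesions".

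Table 8, within Section 8.1.4, requires for irCR that "All measurable lymph nodes have diameter <10 mm in short axis". Its irPR and irPD rows rest on the tumour burden. Appendix D, the irRECIST appendix, also names the short axis for irCR only and gives no axis for the burden.

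**The concern.** A programmer who follows Section 8.1.4 as written will use two axes for the same node: the short axis to decide irCR, and the longest diameter to decide irPR and irPD. The resulting derived responses are then pooled with Phase 2 irRECIST responses assessed by investigators. If investigators measure nodes as Appendix C directs, the irRECIST summaries that include the Phase 1 subjects mix two measurement rules.

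Section 9.3.3 has the same problem for display. The percent-change table and the waterfall plot can place a subject on one side of the 30% line while the investigator's RECIST v1.1 category places the same subject on the other. A reader of the report would have no means of telling a measurement-rule artefact from an assessment error.

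**Working it through.** The SAP states no figure that depends on this definition, so there is none to reproduce. The check is whether the two rules can lead to different categories.

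**Inputs from the SAP**
- Formula (Section 8.1.4): percent change = 100 x (visit sum - reference sum) / reference sum. The reference is baseline for irPR and nadir for irPD.
- Cuts (Table 8): irPR at a decrease of at least 30%; irPD at an increase of at least 20% with a burden of at least 5 mm. Appendix C uses the same percentages for RECIST v1.1, with a minimum absolute increase of 5 mm for PD.
- Rule L (Sections 8.1.4, 9.1, 9.3.3): longest diameter for every lesion.
- Rule S (Appendix C): short axis for nodes, longest diameter for other lesions.

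**Assumed inputs.** The SAP contains no lesion data. The sizes below are illustrations, with nodes written as long x short axis in mm.

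| Case | Rule L | Rule S |
|---|---|---|
| (a) Node 30x20 to 22x12 | (22-30)/30 = -26.7%, SD | (12-20)/20 = -40.0%, PR |
| (b) Node 28x18 to 19x14 | (19-28)/28 = -32.1%, PR | (14-18)/18 = -22.2%, SD |
| (c) Non-nodal 40 to 30, node 30x20 to 22x11 | (52-70)/70 = -25.7%, SD | (41-60)/60 = -31.7%, PR |
| (d) Node from nadir 25x15 to 28x20 | (28-25)/25 = +12.0%, not PD | (20-15)/15 = +33.3%, increase 5 mm, PD |
| (e) Node 30x20 to 21x14 | (21-30)/30 = -30.0% | (14-20)/20 = -30.0% |
| (f) Non-nodal 20 to 0, node 25x16 to 14x9 | (14-45)/45 = -68.9% | (9-36)/36 = -75.0% |

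**Reading the cases**
- (a) and (c): the literal rule misses a response that the Appendix C sum would give.
- (b): it grants a response that the Appendix C sum would not give.
- (d): it misses a progression.
- (e): both axes shrink in proportion, so nothing changes.
- (f): both sums pass the 30% cut. The non-nodal lesion is gone and the node is below 10 mm in short axis, so Table 8's irCR condition for measurable lesions is met whichever sum is used. Only the plotted percentage differs.

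**Weight of one subject.** One reclassified subject moves a response rate by 1/21 = 4.8 points in a set of 21. The irRECIST summaries are not limited to 21 in the ipilimumab arm, where up to 60 may be treated at the RP2D; with 60 in the denominator the shift is 1/60 = 1.7 points.

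**The case against.** **The data may already be right.** Appendix C tells sites to record the short axis for pathological nodes, and Section 8.1.4 draws on the RECIST v1.1 measurable disease page. If the diameter field for a node holds the short axis, the programmed sum is correct and the text merely misnames it. This stands as a real possibility. Against it, the one relevant eCRF item that Table 8 cites by label refers to the longest diameter, so the SAP does not settle the matter.

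**Appendix C governs RECIST v1.1, not irRECIST.** This also stands in part. Appendix D does not say which axis enters the burden, so for Section 8.1.4 the conflict is an inference from the shared baseline target lesions and the shared eCRF page. For Section 9.3.3 the link is more direct, because the lesions summed there are the target lesions that Appendix C defines.

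**Stronger readings that the SAP does not support**
- A reader might infer that the literal rule systematically under-calls response because nodes shrink more in short axis than in length. The SAP says nothing of the kind, and case (b) goes the other way.
- A reader might infer that a nodal responder could never reach a low burden because a normalised node keeps contributing. Appendix C also keeps recording the actual size of nodes below 10 mm, and Table 8 decides irCR by short axis, not by the sum.
- A reader might infer that response and percent change are wrong in every subject with nodal disease, and that the waterfall plot must disagree with RECIST. Only nodal targets and new measurable nodes enter the sums, and the category changes only when the two sums fall on opposite sides of a cut.

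**Conclusion.** The inconsistency is real and should be corrected. Sections 8.1.4, 9.1 and 9.3.3 state a sum that differs from Appendix C whenever a target node is present and, in Section 8.1.4, whenever a new measurable node is added. Applied literally, it can shift a derived irPR or irPD call in either direction, or leave it unchanged.

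The scope is limited to derived irRECIST for Phase 1 subjects at the RP2D (and the pooled summaries that include them), the Phase 1 tumour-burden listing, and the tumour-change summary and waterfall plot of Section 9.3.3. The primary endpoint is the investigator's own RECIST v1.1 assessment, is not computed from this sum and is not affected. Nor are Phase 2 irRECIST responses that investigators assess directly.

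The size in real data cannot be estimated: it depends on nodal measurements and on an eCRF that the SAP does not show. The examples show only that the cuts can be crossed under plausible but assumed sizes. If the diameter field already holds the nodal short axis, the finding reduces to one of wording.

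**What to change.** - In Sections 8.1.4, 9.1 and 9.3.3, and in the specifications for Table 14.2.4.1.2 and Figure 14.2.1, replace the sum of longest diameters with a sum of diameters that takes the longest diameter for non-nodal lesions and the short axis for lymph nodes. Identify nodes from the Location field, as Section 8.1.4 already provides.
- Apply the definition to baseline, visit and nadir burdens and, in Section 8.1.4, to new measurable lesions.
- State the same axis rule for tumour burden in Appendix D.
- Name the eCRF field that holds the nodal short axis.

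The cost is a change of SAP wording and, if the field now holds the longest diameter, a programming change to select the short axis for nodes. Table 8 already needs the nodal short axis to decide irCR, so the value must be available if that rule can be programmed at all; this should be checked against the eCRF first.
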